#### Unlikely:

This category applies to those AEs that, after careful medical consideration, are felt unlikely to be related to the administration of the study TEST product. The relationship of an AE to the study TEST product can be considered unlikely if:

It does not follow a reasonable temporal sequence from administration of the study TEST product.

It could be reasonably explained by the subject's clinical state, environmental or toxic factors or other therapies administrated to the subject.

It does not follow a known pattern of response to the investigational TEST product.

#### Not related:

The AE does not meet any of the above criteria for relatedness.

There is sufficient information that the etiology of the AE is not related to the study TEST product.

#### Not assessable/unclassifiable:

The AE cannot be judged because of insufficient or contradictory information, which cannot be supplemented or verified.

The study conduct relatedness for SAEs will also be assessed and documented. The most likely cause of an SAE (e.g., disease under treatment, concomitant disease, concomitant medication, other) will be indicated on the CRF with details of the concomitant disease or medication or other cause.

#### 9.4 Reporting Procedures

Any AE that meets the criteria for serious outlined in the protocol must be reported to the Medical Monitor within 24 hours from the time site personnel becomes aware of the event. The Medical Monitor Contact Information is:

Medical Monitor [name]

Palm Beach CRO [name] [contact] SAE Fax Line: [contact]

[contact]

Email: [contact]

A written report must be submitted and should consist of the Serious Adverse Event Report Form, accompanied by the following eCRF pages: demographics, medical history AEs, and concomitant medications. If the subject is hospitalized because of or during the course of an SAE, then a copy of the hospital discharge summary *with identifying information removed* should be faxed to SAE Fax line at [contact] or scanned and e-mailed to **[name]**, **MD to** [contact] and/or [name] at: [contact] as soon as it becomes available.

Withdrawal from the study and all therapeutic measures will be at the discretion of the PI, sub-investigator or medical monitor. All SAEs (related or with an unknown relationship to the study TEST product) will be followed until satisfactory resolution or until the PI or sub-investigator deems the event to be chronic or the subject to be stable. All SAEs will be recorded from signing of ICF until the end of the study.

Serious AEs occurring after the end of the study and coming to the attention of the PI must be reported only if they are considered (in the opinion of the PI) causally related to the study TEST product. After receipt of the initial report, the Medical Monitor will review the information and, if necessary, contact the PI, to obtain further information for assessment of the event. The Sponsor or their designated representative will be responsible for all information processing and reporting according to local legal requirements.

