#### Secondary Objective

- 1. To evaluate the safety profile of the Omeza® Products Bundle compared to the standard of care.
- 2. To obtain cost benefit data comparing the Omeza® Products Bundle compared to standard of care in the treatment of chronic venous leg ulcers and diabetic foot ulcers.

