### 3 Study Design

### 3.1 Description of the Study Design

This is a randomized, multicenter, open-label study comparing the Omeza® Products Bundle versus standard of care treatments for 2 different types of chronic ulcers (venous leg ulcers and diabetic foot ulcers). The treatment period will be 12 weeks, with subjects coming into the study site weekly for evaluations, photography and formal measurements of the target wound, and dressing changes. There will be a total of 13 study site visits. The Screening Visit (Day 0) will occur 1 week prior to randomization and will include routine labs and vascular assessment to determine inclusion/exclusion of the potential subject from the study; followed by weekly treatment visits (Week 1 through Week 11); randomization will occur at Treatment Visit Week 1; the Treatment Visit Week 12/End of Study Visit will include end of study labs. Target wounds will be photographed and measured, and vascular assessment will be done at each of the 13 visits. Standard of care will be billed to subject's insurance for both TEST and SOC.

If the wound closes before Week 12, the subject will continue to come in for all the remaining study visits until study completion. If the wound does not close by Week 12, the subject will be immediately exited from the study and no further follow-up will occur as part of the study.

Table 1: Study Plan

Study Period	Visit	Purpose
Screening	Screening (Day 0)	Determine eligibility, routine labs,
		vascular assessment, photos and
		measures
Baseline /	Treatment Visit Week 1	Review eligibility, randomization,
Randomization		Wound-QoL questionnaire, vascular
		assessment, photos and measures,
		begin study treatments.
Treatment	Treatment Visits Week 2 - Week	Study treatments, vascular assessment,
	11	photos and measures
End of Study Visit	Treatment Visit Week 12	End of Study routine labs, vascular
		assessment, photos and measures,
		Wound-QoL questionnaire

For subject to be eligible they must meet entry criteria. If the subject is not found eligible at Treatment Visit Week 1, the subject may be re-screened once or may be replaced.

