### 9 Assessment of Safety

### 9.1 Adverse Event Recording/Documentation

At each contact with the subject, information regarding adverse events will be elicited by appropriate questioning and examinations. All events, both expected/unexpected and related/unrelated will be recorded on a source document. Source documents will include progress notes, laboratory reports, consult notes, phone call summaries and data collection tools. Source documents will be reviewed in a timely manner by the research team. All reportable adverse events that are identified will be recorded on the eCRF. The start date, the stop date, the severity of each reportable event, the PI's judgment of the AEs relationship and expectedness to the TEST products and the outcome will also be recorded. Adverse event reporting will extend from signing of ICF until completion of final visit.

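### Follow-up of SAEs still open at exit depends on relationship to the TEST product, hence on arm, and the follow-up rule conflicts with the Week 12 exit sentence

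*Protocol*

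**What the plan says.** Three sets of statements in the protocol bear on this.

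- **Reporting and recording.** Section 9.4: "Any AE that meets the criteria for serious outlined in the protocol must be reported to the Medical Monitor within 24 hours". It adds: "All SAEs will be recorded from signing of ICF until the end of the study". Section 9.1 has related and unrelated events alike entered on a source document, lists outcome among the recorded items, and fixes the window: "Adverse event reporting will extend from signing of ICF until completion of final visit". None of these carries a condition on arm or relationship.
- **Follow-up of SAEs.** Section 9.4: "All SAEs (related or with an unknown relationship to the study TEST product) will be followed until satisfactory resolution". The same sentence also lets follow-up stop once an investigator regards the event as chronic or the subject as stable.
- **Week 12 exit.** For a subject whose wound has not closed by Week 12, Section 3.1 says that "the subject will be immediately exited from the study and no further follow-up will occur as part of the study". The synopsis, Section 6.4 and a footnote to Appendix B say the same. None makes an exception for an ongoing SAE.

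Safety is a comparative objective. The first secondary objective in Section 2 opens "To evaluate the safety profile of the" and goes on to set the bundle against standard of care.

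**The concern.** The follow-up rule is tied to a product that only one arm receives. Section 9.3 has the investigator grade causality against the TEST product, and the SOC steps in Appendices 2 and 3 contain no Omeza product. An SAE in a correctly treated SOC subject would normally be graded as not related, so nothing in 9.4 requires it to be pursued past the final visit. In the TEST arm the same event would be pursued or not according to the investigator's causality judgement, made with the treatment known.

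The Week 12 sentence raises a second problem. A site with a qualifying SAE still open in a subject with an unclosed wound is told both to follow the event and to follow nothing further.

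At stake is the completeness of the outcome field for the SAEs that last longest, in a trial that sets out to compare safety between arms. Section 9.9 also lists the treatment of adverse reactions among the costs to be compared. It states no time horizon, so I put no weight on that.

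**Working it through.** No figure in the protocol bears on this point, so the check is a comparison of passages.

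**Step 1. What does not depend on arm.** 24-hour reporting, recording of SAEs from consent to end of study, and recording of outcome to the final visit (9.1, 9.4) apply to everyone. Both arms have the same weekly visits with adverse event monitoring (Section 6, Appendix B). Subjects who withdraw are to have the end-of-study evaluations where possible (4.3.3, 9.7).

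**Step 2. What does depend on arm.** Only the instruction to keep following an SAE to an endpoint is conditioned on relationship to TEST.

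**Step 3. Where this makes a difference.**

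| SAE | Resolved by final visit | Open at final visit or withdrawal |
|---|---|---|
| TEST, related or unknown relationship | Outcome recorded | Followed until resolved, chronic or stable |
| TEST, judged unrelated | Outcome recorded | No follow-up required by 9.4 |
| SOC | Outcome recorded | Normally no follow-up required by 9.4 |

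The arms differ only in the right-hand column.

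**Step 4. How firm the trigger is within TEST.** Section 9.3 defines six categories: Related, Probable, Possible, Unlikely, Not related, and Not assessable/unclassifiable. Section 9.4 speaks of related or unknown relationship. It does not say whether Probable or Possible events qualify, and unknown is not one of the six. Section 10.3 uses yet another cut, at least possible. Two investigators could apply 9.4 differently to the same event.

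**Step 5. The Week 12 sentence.** Take a subject with an unclosed wound and an SAE of related or unknown relationship that is neither resolved, chronic nor stable at the Week 12 visit. Section 9.4 requires follow-up to continue. Sections 3.1 and 6.4, the synopsis and Appendix B say that none will occur within the study. Both cannot be met. The condition is wound status and no arm is named, so this is a contradiction and not an arm-specific rule.

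**Step 6. Size.** Planned SOC subjects: 13 + 13 = 26. Planned TEST subjects: 26 + 26 = 52. Total: 26 + 52 = 78. These are the subjects to whom each version of the rule applies, not a count of affected events. That count needs the SAE rate and the fraction of SAEs still open at exit. For Step 5 it also needs the fraction of wounds unclosed at Week 12. The protocol gives none of these.

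**The case against.** The strongest reply is that very little data are touched. Every SAE in either arm is reported, recorded and given an outcome up to the final visit. An SOC event that resolves in the study is documented exactly like a TEST event. Even TEST follow-up may stop once the event is deemed chronic or the subject stable. Section 10.3 plans a listing of subjects with SAEs and states no between-arm comparison of SAE duration or outcome. All of this stands, and it sets the limits of the point.

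A reader might infer that SAE outcomes as a whole cannot be compared between arms, or that every SAE in the 26 SOC subjects is lost to follow-up. The documents do not support that, for the reasons just given. A reader might also infer that the Week 12 sentence biases the safety comparison. It names no arm and applies only to unclosed wounds. It could act unevenly only if closure rates differed, and the protocol gives no figure from which to argue that.

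It can also be said that the 9.4 sentence begins by referring to all SAEs, so the parenthesis need not restrict it. Restriction is still the natural reading: the neighbouring reporting and recording sentences have no such parenthesis, and read otherwise it would do nothing. If the wording is ambiguous, sites still need it settled. Section 9.3 does ask for study-conduct relatedness and the most likely cause of each SAE, but 9.4 does not use either to decide who is followed.

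Finally, the exit sentence can be read as ending wound visits only, with 9.4 as the specific safety rule. That may be the intention, but the sentence does not say so in any of its four places.

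**Conclusion.** The point holds in a limited form. As written, the final outcome of an SAE still open at the final visit or withdrawal is pursued under a rule that depends on arm and, within TEST, on an open-label causality call. Separately, 9.4 and the Week 12 exit sentence contradict each other for a qualifying SAE open at that visit in a subject with an unclosed wound.

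This rests on two assumptions: that the parenthesis in 9.4 restricts the rule, and that SAEs in SOC subjects would normally be graded as not related to a product they did not receive. The number of events affected cannot be stated from the protocol, and no analysis described in Section 10.3 is shown to change. The sentence in 9.4 on SAEs arising after the end of the study, which "must be reported only if they are considered (in the opinion of the PI) causally related to the study TEST product", uses the same reference product. It concerns new events outside the 9.1 window and is not part of this point.

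**What to change.** Reconcile Section 9.4 with Sections 3.1 and 6.4, the synopsis and the Appendix B footnote by amendment, so that:

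- capture of safety data for SAEs open at the final visit or withdrawal follows one rule that depends neither on arm nor on assessed relationship to TEST; and
- the Week 12 exit sentence states, in all four places, whether it applies to SAEs ongoing at exit.

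This concerns data capture only; treatment and clinical care of the event are not at issue. The cost is amendment wording and a few extra contacts by existing site staff for SAEs still open.

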### 9.5 Pregnancy

If a female subject is or should become pregnant during the study (i.e., from the date the ICF was signed until the subject's last visit), the PI (or authorized delegate) should notify the Medical Monitor on the initial Pregnancy Report Form within 24 hours of the PI or site personnel first becoming aware of the pregnancy. Pregnancy itself is not an AE, unless there is suspicion that the investigational TEST product may have interfered with the effectiveness of a contraceptive medication.

All reports of congenital abnormalities/birth defects are SAEs. Spontaneous miscarriages should also be reported and handled as SAEs. However, elective abortion without complications should not be handled as SAEs.

All outcomes of pregnancy must be reported by the PI to the Medical Monitor on the pregnancy outcome report form within 30 days after he/she has gained knowledge of the normal delivery or elective abortion.

### 9.6 Premature Termination of the Study

If the PI, the sponsor, and/or the Medical Monitor become aware of conditions or events that suggest a possible hazard to subjects if the study continues, the study may be terminated after appropriate consultation between the relevant parties. The study may also be terminated early at the sponsor's discretion in the absence of such a finding. Conditions that may warrant termination include, but are not limited to:

- The discovery of an unexpected, significant, or unacceptable risk to the subjects enrolled in the study.
- Failure to enroll subjects at an acceptable rate.
- A decision on the part of the sponsor to suspend or discontinue development of the study TEST product.

If a significant safety issue is identified, either from an individual case report or review of aggregate data, then the sponsor, in consultation with its advisors, will issue prompt notification to all PIs and IRBs. A significant safety issue is one that has a significant impact on the course of the clinical study or program (including the potential for suspension of the development program or amendments to protocols) or warrants immediate update of informed consent.

### 9.7 Early Withdrawal of a Subject

If a subject is prematurely withdrawn from the study for any reason, the PI should record the reason(s) for withdrawal and make every effort to perform the evaluations described for the end of study visit.

## 9.8 Replacement of a Subject Who Discontinues Study Treatment

Subjects who met entry criteria and have been randomized will not be replaced if they drop out from the study for any reason.

#### 9.9 Cost Benefit Assessment

The acquisition price from a supplier may be the most basic cost of a product but is not the complete cost of product utilization. When choosing between different products of the same category for Medical Policy development, the Med Tech Committee will want to know the overall cost of using the product, not merely the price of an individual application. There are three types of cost associated with product use in a health-care system: direct, indirect and intangible.

- 1. The Direct costs include:
  - Acquisition cost of the device (Omeza® Lidocaine Lavage, Omeza® Collagen Matrix and Omeza® Skin Protectant)
  - Supplies to administer the medicine
  - Standard of Care, topical anaesthetic, saline, collagen alginate, foam, soft roll, compressive wrap
  - Pharmacist salary, preparation and dispensing of medications, clinical pharmacy activities, nursing salaries, physician fees

- 2. The Other Direct costs include:
  - Treating adverse reactions
  - Inpatient and outpatient treatment of poor response to therapy, emergency room use
  - Hospital overhead costs, for example electricity laboratory services
- 3. The Indirect costs include:
  - Cost of illness to the patient
  - Lost time from work
- 4. The intangible costs include:
  - Quality of life

# 10 Statistical Considerations (See Statistical Analysis Plan [SAP])

### 10.1 General Considerations and Populations

The primary endpoint is percent change from baseline in target wound measure by Week 12/End of Study.

All statistical testing will be performed at a two-sided alpha=0.05 level of significance. A detailed Statistical Analysis Plan (SAP) will be finalized prior to database lock.

All subjects who are randomized and receive at least one study treatment will be included in the Safety Population. All summaries of safety data will be based on this population and reported "as treated" – in case there are subjects that were not treated as per the randomization outcome.

All subjects who are randomized, receive at least one study treatment and have at least one post-baseline measure assessment will be included in the Intent-to-Treat Population (ITT). All efficacy summaries will be based on this population and will be reported according to the intent to treat principle (as randomized).

A review of major protocol violations will be performed. Major violations will include, but not be limited to, an assessment of compliance, use of concomitant medications and intercurrent illnesses. Subjects and data points without major protocol violations will be included as part of the Per-Protocol Population. If fewer than 10% of the subjects have major protocol violations, these analyses may not be performed.

All analyses and summaries will be reported overall and for each indication (venous leg ulcers and diabetic foot ulcers).

## 10.2 Efficacy Analyses

Primary and Secondary Efficacy Analysis

1. The null hypothesis to be tested for the primary efficacy endpoint is: No differences between the TEST (Omeza® Products Bundle) and the Standard of Care.

The primary efficacy endpoint, percent change of wound measure from baseline at Week 4, Week 8 and by Week 12 will be analyzed using mixed model repeated measure (MMRM) with fixed effects factors of treatment and visit and subject as a random effect in the statistical model.

- 2. Time to maximum closure or complete closure can be defined as the time taken from the start of treatment till the closure (complete or maximum) of the ulcer. Time to closure data will be analyzed using Kaplan Meier Product Life Estimate with median, guartiles and 95% CI.
- 3. Wound reduction rate will be calculated at Week 4, 8 and by Week 12.
- 4. Proportion of subjects healed at Week 12 will be compared between TEST (Omeza® Products Bundle) and SOC.

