## 10.4 Sample Size Rationale

The power of the study is computed for the primary endpoint of "percent change from baseline in target wound measure by Week 12" comparing the two means. The combined sample size of 78 subjects (randomized 2:1) will provide over 80% power to detect a difference of about 14 units (percent change from baseline in wound measure by Week 12), assuming a standard deviation of 20 units, and a 2-sided significance level of 5%.

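### The primary MMRM as written tests a treatment difference averaged over visits, while Sections 10.1 and 10.4 define and power the endpoint at Week 12

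*Protocol*

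**What the plan says.** The protocol describes its primary endpoint in two ways.

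- **Week 12 only.** Section 10.1: "The primary endpoint is percent change from baseline in target wound measure by Week 12/End of Study". Section 10.4 powers a comparison of two means by Week 12: "The combined sample size of 78 subjects (randomized 2:1) will provide over 80% power to detect a difference of about 14 units", with an SD of 20 and a two-sided 5% level.
- **Three timepoints.** Section 10.2: "The primary efficacy endpoint, percent change of wound measure from baseline at Week 4, Week 8 and by Week 12 will be analyzed" by MMRM. The Statistical Methods part of the Synopsis and Section 3.2 also list Weeks 4, 8 and 12 under the primary endpoint.

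The model is stated outright. Section 10.2 says the data "will be analyzed using mixed model repeated measure (MMRM) with fixed effects factors of treatment and visit and subject as a random effect". It lists no treatment-by-visit interaction and names no Week 12 contrast. The null hypothesis is one of no difference between the arms and gives no timepoint. The Synopsis adds no further model term.

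**The concern.** A model with treatment and visit as its only fixed effects forces the same treatment difference at every visit. Its only treatment test is therefore a visit-averaged one, and the Week 12 difference that Sections 10.1 and 10.4 rely on is not among its parameters.

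Two consequences are possible. If benefit builds up over time, the averaged target is smaller than the Week 12 effect used for the power calculation. If benefit appears early and fades, the primary test can reject although the arms do not differ at Week 12.

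This is not a detail left to the SAP, because the protocol has already listed the fixed effects. An SAP that follows the list inherits the mismatch. An SAP that departs from it would choose the primary test as late as just before database lock (Section 10.1), in an open-label study.

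**Working it through.** **Inputs from the protocol.** 78 subjects, 2:1, so 52 TEST and 26 SOC (26/13 per indication); difference 14; SD 20 at Week 12; two-sided 5% (Section 10.4 and Synopsis). Baseline is Treatment Visit Week 1 (Synopsis), so Weeks 4, 8 and 12 fall 3, 7 and 11 weeks after baseline.

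**Assumptions, since the protocol gives no values.** The course of the effect over visits, the SDs before Week 12, and the within-subject correlation r, taken as 0.4, 0.6 and 0.8 and equal for all pairs of visits. Data are complete.

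**1. The plan's own figure.** SE = 20 × √(1/26 + 1/52) = 4.80. With 14/4.80 = 2.91 as noncentrality on 76 df, power is 82.1% (83.0% by the normal approximation). The stated figure of over 80% is reproduced, for a Week 12 comparison of means.

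**2. What the stated model estimates.** With complete data and a random subject intercept, the treatment coefficient is the equally weighted mean of the visit differences. Its per-subject SD is the SD of the mean of the three visits:

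- equal SDs: 20 × √((1 + 2r)/3), giving 15.5, 17.1 and 18.6 for r = 0.4, 0.6 and 0.8;
- unequal SDs s₁, s₂, s₃: (1/3) × √(Σsᵢ² + 2rΣsᵢsⱼ), the second sum over pairs of visits.

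**3. Linear growth to 14 at Week 12.** The effects are 14 × 3/11 = 3.8, 14 × 7/11 = 8.9, and 14.0. Their average is 14 × (3 + 7 + 11)/33 = 8.9.

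**4. Power of the stated model** (noncentral t, 52/26):

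| Effects at Weeks 4, 8, 12 | SDs at Weeks 4, 8, 12 | r = 0.4 | r = 0.6 | r = 0.8 |
|---|---|---|---|---|
| 3.8, 8.9, 14.0 | 20, 20, 20 | 66% | 57% | 50% |
| 3.8, 8.9, 14.0 | 10, 15, 20 | 88% | 81% | 74% |
| 3.8, 8.9, 14.0 | 5.5, 12.7, 20 (proportional to time) | 95% | 91% | 87% |
| 14, 14, 14 | 20, 20, 20 | 96% | 92% | 87% |

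The comparator for every row is 82% for the Week 12 contrast.

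**5. Rejection when there is no Week 12 difference.** Effects 12, 6 and 0 average 6. The stated model rejects 36%, 30% and 26% of the time at SD 20, and 56%, 48% and 42% with SDs 10, 15, 20. A Week 12 test would reject 5% of the time.

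**6. Simulation check.** 300 simulated trials with linear growth, SD 20 and r = 0.5 gave a mean main-effect estimate of 8.7 with 65% rejection. The Week 12 contrast from a model with the interaction gave 13.6 with 83% rejection. The closed form for the main effect at r = 0.5 is 61–62%, within simulation error (√(0.65 × 0.35/300) = 2.8 points).

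**7. If all weekly visits from Week 2 to Week 12 enter the model**, the linear-growth target becomes 14 × 6/11 = 7.6. With missing visits the weights are no longer exactly equal.

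**The case against.** The strongest reply is that the model fits the three-timepoint wording in the Synopsis, Section 3.2 and Section 10.2, and that only Sections 10.1 and 10.4 single out Week 12. That is correct. It means the endpoint wording itself must be reconciled, and a visit-averaged endpoint would be a legitimate choice. It does not rescue the plan as it stands, because the power calculation is for Week 12.

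A reader might infer that the trial loses its stated power. The protocol does not support that. The 50–66% range needs both linear growth and an SD of 20 at every visit, while Section 10.4 gives SD 20 for Week 12 only. Percent change starts at zero for everyone, so smaller early SDs are plausible; the loss then shrinks or reverses. With a constant effect the averaged test is the more powerful one.

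A reader might also infer that the random-intercept covariance, or the absence of covariates, invalidates the test. Neither follows. With complete data the main-effect test compares subject means and is valid whatever the within-subject covariance, provided the arms share it. Covariance matters once visits are missing or a Week 12 contrast is tested. Omitting indication and baseline area does not bias a randomized comparison, and the protocol also plans analyses within each indication.

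**Conclusion.** The mismatch of target is certain and follows from the model terms as stated: the primary test in Section 10.2 does not test the endpoint of Sections 10.1 and 10.4 unless the treatment difference is constant over visits. It should be corrected before the analysis is fixed.

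The size of the consequence is not determined by the protocol. Across the linear-growth cases examined, power runs from 50% to 95% against 82% for the Week 12 contrast, so it may fall or rise. The fading case is less equivocal about interpretation: under the assumed effects of 12, 6 and 0, the test rejects 26–56% of the time over the two SD patterns shown, and a reader of Section 10.1 would take that as a Week 12 result. Confidence is high in the mismatch and limited in any single power figure.

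**What to change.** - **Section 10.2:** add a treatment-by-visit term and name the Week 12 TEST-minus-SOC contrast as the single primary test. Use a within-subject covariance that lets variance and correlation differ by visit.
- **Synopsis (Statistical Methods), Section 3.2 and Section 10.2:** align the primary endpoint wording with Sections 10.1 and 10.4, leaving Weeks 4 and 8 as supporting timepoints.
- **Alternative:** keep the main-effects model and redefine the endpoint in 10.1 and the power calculation in 10.4 as a visit average, stating which visits enter and the assumed effects, SDs and correlation.
- **Optional:** adjust the overall analysis for indication and baseline wound area, both already collected. If they explain an assumed 10–20% of the variance, the SD falls to 20 × √0.9 = 19.0 or 20 × √0.8 = 17.9, and Week 12 power rises from 82% to about 86–90%.

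The cost is wording and a few model degrees of freedom, with no new data. The Week 12 contrast gives up the power advantage that the averaged test would have if the effect were constant (82% against 87–96% at SD 20).
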